4.2.3. Definition of Dose-Limiting Toxicity of Cetuximab and Nivolumab

The phase I of the study will enroll 3 to 6 patients per dose level using a standard 3+3 design. The DLT period will start on Cycle 1 Day 1 of cetuximab and nivolumab and end on Cycle 1 Day 28. The toxicity after the lead-in cetuximab (Day -14 before Cycle 1 only) prior to the dosing of cetuximab and nivolumab will not be included to the assessment of DLT (Day -14 to Day -1).

The MTD will be determined using the following de-escalation rules:

- A cohort of three patients will be entered at Dose Level 1.
- If none of these patients experiences a DLT (see below for the criteria) during Cycle 1 (4 weeks), Dose Level 1 will be the recommended dose for Phase II.
- If 1 of these 3 patients experiences a DLT, 3 more patients will be enrolled at Dose Level 1. If 1 of 6 patients at this dose level experiences a DLT, the phase II dose will be Dose Level 1. If 2 or more DLTs occur within Dose Level 1, then the MTD will have been exceeded, and 6 new patients will be enrolled at Dose Level -1.
- If ≤1 of 6 patients at Dose Level -1 experiences a DLT, the phase II dose will be Dose Level -1. If 2 or more DLTs occur within Dose Level -1, then the MTD will have been exceeded. This combination is determined to be unsafe to conduct the phase II portion of the trial and the trial will be discontinued.

The target DLT rate is <25%. The MTD will be defined as the dose of cetuximab and nivolumab in which <1 of 3 patients experience a DLT or <2 of 6 patients experience a DLT with the next higher dose having at least 2 patients experiencing a DLT. The MTD is the highest dose at which at most 1 of 6 patients has a DLT.

IND#: Exempt

No dose escalations or de-escalations are permitted within each patient's treatment, although dose delays will be permitted. A patient who is withdrawn from the study before the completion of Cycle 1 for a reason other than a DLT will be replaced.

This study will utilize the Cancer Therapy Evaluation Program Common Terminology Criteria for Adverse Events (CTCAE) version 4.1 for toxicity and event reporting. DLTs will be observed until patients have completed Cycle 1 (4 weeks).

A DLT will be defined as any of the following events:

- Grade 3 or 4 immune-related toxicities, including dermatitis, hepatitis, thyroiditis, colitis, and pneumonitis.
- Grade 4 cetuximab-related rash.

Study Number: MCC 19178

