4.4.1. Dose Modifications for Cetuximab-related Immunological Toxicities

If the patient experiences any drug-related event \leq Grade 2, the dose of cetuximab and nivolumab should be continued at the given dose level.

If the patient experiences any drug-related event ≥ Grade 3, the dose of cetuximab and nivolumab should be discontinued until resolution of the toxicities to grade 1 or baseline. Upon restarting, the physician may choose to reduce the dose of Cetuximab per the dose reduction table below.

In the event of a prolonged (≥7 consecutive days) Grade 2 drug-related toxicities, the investigator may choose to pause cetuximab and nivolumab for up to 4 weeks to allow the patient to recover followed by a dose reduction (the hold and reduction are both at the treating physician's discretion). Only the cetuximab may be dose reduced, and dose reductions are according to the following table:

	Cetuximab	Nivolumab
	Cycles 1-24 (Q 2 weeks)	Cycles 1-24 (Q 2 weeks)
Dose Level 1	500 mg/m ²	240 mg
Dose Level -1	250 mg/m ²	240 mg
Dose Level -2	125 mg/m ²	240 mg

For cetuximab-related toxicity, treatment with oral/IV corticosteroids is allowed only for toxicities ≥ Grade 3.

Use of corticosteroids (≤ 10 mg daily prednisone equivalents) is allowed. Inhaled or topical steroids and adrenal replacement doses > 10 mg daily prednisone equivalents are permitted in the absence of active autoimmune disease.

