4.4.2. Dose Modifications for Cetuximab-related Non-Immunological Toxicities

If the patient experiences any drug-related event \leq Grade 2, the dose of cetuximab and nivolumab should be continued at the given dose level.

If the patient experiences any drug-related event ≥ Grade 3, the dose of cetuximab and nivolumab should be discontinued until resolution (to baseline) of the toxicities, or until stabilization. Upon resumption, the physician may choose to reduce the dose of Cetuximab per the table below. As an exception, continued treatment in the face of Grade 3 hypomagnesemia and hypophosphatemia will be allowed at the treating physician's discretion. Low magnesium is expected while treating with cetuximab and can be safely replenished as needed throughout treatment according to local guidelines.

If the patient experiences any acute onset or worsening pulmonary symptoms, the doses of cetuximab and nivolumab should be delayed. The management should follow the pulmonary toxicity management as detailed in Section 4.5 Table 2 Pneumonitis and Appendix 4 Pulmonary Adverse Event Management Algorithm because interstitial lung disease from cetuximab and pneumonitis from nivolumab cannot be reliably distinguished.

IND#: Exempt

In the event of Grade ≥ 3 rash, treatment with cetuximab should be paused until recovery to Grade ≤ 2 . Treatment should be resumed at a reduced dose (see Section 4.3). If Grade ≥ 3 rash does not resolve to Grade ≤ 2 within 14 days of stopping cetuximab treatment and despite optimal supportive care, the patient should not receive any further treatment with cetuximab.

In the event of a prolonged (≥7 consecutive days) Grade 2 drug-related toxicities, the investigator may choose to pause cetuximab and nivolumab for up to 4 weeks to allow the patient to recover followed by a dose reduction (the hold and reduction are both at the treating physcian's discretion). Only the cetuximab may be dose reduced, and dose reductions are according to the following table:

	Cetuximab	Nivolumab
	Cycles 1-24 (Q 2 weeks)	Cycles 1-24 (Q 2 weeks)
Dose Level 1	500 mg/m ²	240 mg
Dose Level -1	250 mg/m ²	240 mg
Dose Level -2	125 mg/m ²	240 mg

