		grade 0-1. Therapy	resolve within 12
		with nivolumab can be continued while	weeks of last dose or inability to reduce
		endocrine	corticosteroid to 10
		replacement therapy	mg of prednisone or
		is instituted	equivalent per day
			within 12 weeks
	4		Permanently
Infusion Reaction	22	Toxicity resolves to	discontinue
IIIIUSIOII REACTIOII	Z-	Grade 0-1	Permanently discontinue if toxicity
			develops despite
			adequate
			premedication
	3–4	Permanently	Permanently
Dm		discontinue	discontinue
Pneumonitis	2	Toxicity resolves to	Toxicity does not resolve within 12
		grade 0-1	weeks of last dose
			or inability to reduce
			corticosteroid to 10
	L	L	continuositationa to 10

discontinue

			mg of prednisone or equivalent per day within 12 weeks
	3-4	Permanently discontinue	Permanently discontinue
Renal Failure or Nephritis	2	Toxicity resolves to grade 0 -1	Toxicity does not resolve within 12 weeks of last dose or inability to reduce corticosteroid to 10 mg of prednisone or equivalent per day within 12 weeks
	3-4	Permanently discontinue	Permanently discontinue
All Other Drug- Related Toxicities ³ .	3	Toxicity resolves to grade 0 -1	Toxicity does not resolve within 12 weeks of last dose or inability to reduce corticosteroid to 10 mg of prednisone or equivalent per day within 12 weeks
	4	Permanently	Permanently

IND#: Exempt

Note: Permanently discontinue for any severe or Grade 3 drug-related AE that recurs or any life-threatening event.

1. For patients with liver metastasis and who begin treatment with Grade 2 AST or ALT, if AST or ALT increases by greater than or equal to 50% relative to baseline and lasts for at least 1 week, then patient should be discontinued.

discontinue

- 2. If symptoms are resolved within one hour of stopping drug infusion, the infusion may be restarted at 50% of the original infusion rate for the next scheduled dose.
- 3. Patients with intolerable or persistent Grade 2 drug-related AE may hold study medication at physician's discretion. Study drug should be permanently discontinued for persistent Grade 2 adverse reactions for which treatment with nivolumab has been held that do not recover to Grade 0-1 within 12 weeks of the last dose.

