4.6.1 Steroids

Treatment with oral/IV corticosteroids (>10mg daily prednisone equivalent) is not allowed for non-immunological toxicities. Treatment with oral/IV corticosteroids (>10mg daily prednisone equivalent) for immunological toxicities is permitted as detailed in the dose modification sections.

Use of corticosteroids (≤ 10 mg daily prednisone equivalents) is allowed. Inhaled or topical steroids and adrenal replacement doses > 10 mg daily prednisone equivalents are permitted in the absence of active autoimmune disease.

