Rule out non-inflammatory causes. If non-inflammatory cause, treat accordingly and continue I-O therapy. Evaluate with imaging and pulmonary consultation.

[figure not shown]

Patients on IV steroids may be switched to an equivalent dose of oral corticosteroids (e.g. prednisone) at start of tapering or earlier, once sustained clinical improvement is observed. Lower bioavailability of oral corticosteroids should be taken into account when switching to the equivalent dose of oral corticosteroids.

Updated 05-Jul-2016

Hepatic Adverse Event Management Algorithm

Rule out non-inflammatory causes. If non-inflammatory cause, treat accordingly and continue I-O therapy. Consider imaging for obstruction.

Patients on IV steroids may be switched to an equivalent dose of oral corticosteroids (e.g. prednisone) at start of tapering or earlier, once sustained clinical improvement is observed. Lower bioavailability of oral corticosteroids should be taken into account when switching to the equivalent dose of oral corticosteroids.
*I-O therapy may be delayed rather than discontinued if AST/ALT ≤ 8 x ULN or T.bili ≤ 5 x ULN.

[figure not shown]
^{**}The recommended starting dose for grade 4 hepatitis is 2 mg/kg/day methylprednisolone IV.

Study Number: MCC 19178

IND#: Exempt

Endocrinopathy Management Algorithm

[figure not shown]
Rule out non-inflammatory causes. If non-inflammatory cause, treat accordingly and continue I-O therapy. Consider visual field testing, endocrinology consultation, and imaging.

Patients on IV steroids may be switched to an equivalent dose of oral corticosteroids (e.g. prednisone) at start of tapering or earlier, once sustained clinical improvement is observed. Lower bioavailability of oral corticosteroids should be taken into account when switching to the equivalent dose of oral corticosteroids.

Skin Adverse Event Management Algorithm

Rule out non-inflammatory causes. If non-inflammatory cause, treat accordingly and continue I-O therapy.

[figure not shown]

Patients on IV steroids may be switched to an equivalent dose of oral corticosteroids (e.g. prednisone) at start of tapering or earlier, once sustained clinical improvement is observed. Lower bioavailability of oral corticosteroids should be taken into account when switching to the equivalent dose of oral corticosteroids. *Refer to NCI CTCAE v4 for term-specific grading criteria.

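### The steroid limits in 4.4.1 and 4.6.1 carry no exception for the Grade 2 lung events that 4.4.2 sends to steroid-based pneumonitis management

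*Combined protocol and SAP*

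**What the plan says.** Two sections limit systemic steroids.

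- Section 4.4.1 (cetuximab-related immunological toxicities): "For cetuximab-related toxicity, treatment with oral/IV corticosteroids is allowed only for toxicities ≥ Grade 3". The relief beside it is that "Use of corticosteroids (≤ 10 mg daily prednisone equivalents) is allowed", together with inhaled or topical steroids and adrenal replacement.
- Section 4.6.1: "Treatment with oral/IV corticosteroids (>10mg daily prednisone equivalent) is not allowed for non-immunological toxicities". For immunological toxicities it permits such doses in the way the dose-modification sections set out.

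A third section directs how lung events are managed. Section 4.4.2 (cetuximab-related non-immunological toxicities) has both drugs delayed for lung symptoms that are acute in onset or worsening, and adds: "The management should follow the pulmonary toxicity management as detailed in Section 4.5 Table 2 Pneumonitis and Appendix 4 Pulmonary Adverse Event Management Algorithm". Its reason is "because interstitial lung disease from cetuximab and pneumonitis from nivolumab cannot be reliably distinguished".

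That instruction leads to two places.

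- Section 4.5, Table 2, pneumonitis, Grade 2: treatment is held until Grade 0-1. Nivolumab is stopped if the event has not resolved within 12 weeks of the last dose, or if the steroid cannot be brought down to 10 "mg of prednisone or equivalent per day within 12 weeks".
- Appendix 4, pulmonary page, in the text that survives: "Patients on IV steroids may be switched to an equivalent dose of oral corticosteroids (e.g. prednisone) at start of tapering or earlier".

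On classification, the dose-limiting toxicity list in 4.2.3 includes "Grade 3 or 4 immune-related toxicities, including dermatitis, hepatitis, thyroiditis, colitis, and pneumonitis", so pneumonitis is treated there as immune-related.

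**The concern.** The investigator is told to manage a Grade 2 lung event on a pathway that expects steroid doses above 10 mg/day. Two other sections, read literally, do not allow such doses if the event is put down to cetuximab. Nothing states which instruction gives way.

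Two practical consequences follow. Care given as 4.4.2 directs could be logged as a deviation, and the three sites could log it differently. A site that gives weight to the explicit limit could also withhold or delay steroids for an event that may be nivolumab pneumonitis. This concerns safety management and deviation classification, not the survival analysis.

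**Working it through.** No arithmetic applies. The check sets the instructions side by side for one case: a Grade 2 lung event treated with more than 10 mg/day prednisone equivalent.

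1. **Is the event covered by the lung instruction?** Yes. The trigger in 4.4.2 has no minimum grade.

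2. **Does the pathway presuppose more than 10 mg/day at Grade 2?** Yes, by inference. A criterion about failing to come down to 10 mg/day has meaning only for a patient above that dose, so the low-dose allowance in 4.4.1 does not cover it. The pulmonary page speaks of IV steroids, an oral switch and a taper, and the opening of Appendix 4 describes steroids as a primary therapy. The grade-by-grade pulmonary flowchart is not shown, so the Grade 2 starting dose cannot be read.

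3. **Which limits reach the event?**

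| Attribution and class | 4.4.1 | 4.6.1 |
|---|---|---|
| Cetuximab, immunological (as 4.2.3 lists pneumonitis) | Below the Grade 3 floor, so not allowed | Allowed as the dose-modification sections provide; these include 4.4.1 but also 4.4.2 and 4.5 |
| Cetuximab, non-immunological (as 4.4.2 is headed) | Not allowed by the sentence's wording; not reached if the section heading confines it | Not allowed |
| Nivolumab alone, immunological | Not reached | Allowed as the dose-modification sections provide |

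4. **How far up the grades does it go?** Grades 3 and 4 meet the 4.4.1 floor, so the clash with that section stops at Grade 2. The 4.6.1 bar has no grade term and turns on classification alone.

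5. **Does any text lift the limits for lung events?** None was found. The lung paragraph in 4.4.2 does not mention steroids, 4.4.1 or 4.6.1. The protocol does write exceptions out elsewhere: 4.4.2 makes one for Grade 3 hypomagnesemia and hypophosphatemia, and both steroid sections make one for adrenal replacement. The protection from deviations in 4.4 and 4.5 covers treatment delays for symptoms the protocol does not specify and unavailability through hospitalization. It does not cover steroid use.

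**The case against.** The strongest reply is that the lung paragraph already works as a specific exception. Section 4.4.2 otherwise continues both drugs for any drug-related event at Grade 2 or below, yet the lung paragraph delays both drugs at any grade. A site must therefore already read it as overriding the rules around it, and reading the steroid sentence the same way is a short step. The stated reason for the instruction is that the two causes cannot be told apart, so management is meant to be the same whatever the attribution. Section 4.6.1 can be read in support, because the dose-modification sections it defers to include 4.4.2 and 4.5. Table 2 also prescribes no steroid: the 10 mg/day wording is one arm of a stopping criterion that recurs in several other rows. Appendix 4 describes itself as guidance.

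Most of this stands. It makes the intent fairly clear and the harm conditional on a literal reading. It does not remove the inconsistency, because the 4.6.1 permission leads to 4.4.1 as readily as to 4.4.2, and neither limit yields in terms.

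A reader might infer more, namely that the protocol forbids effective steroid treatment of Grade 2 pneumonitis, or makes compliance depend wholly on an attribution it calls unreliable. The documents do not support that: the lung instruction is there to make management independent of cause, and an event attributed to nivolumab alone meets neither limit.

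A reader might also infer a matching conflict in 4.4.3, which allows corticosteroids for late hypersensitivity symptoms without grade, route or dose. That would clash with 4.4.1 only if systemic doses above 10 mg/day were used below Grade 3. Section 4.4.3 also lets its recommendations be adapted to local standards. It does not justify a general exemption for infusion reactions.

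**Conclusion.** The point holds as a minor correction to safety text. For a Grade 2 lung event attributed to cetuximab and given more than 10 mg/day, the care that 4.4.2 directs can be read as contrary to 4.4.1 or 4.6.1, depending on how the event is classed.

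This rests on two things: the inference from the Table 2 stopping criterion that Grade 2 treatment exceeds 10 mg/day, and the absence of any sentence giving the lung instruction priority. If the flowchart that is not shown gives no systemic steroid at Grade 2, the practical conflict would be narrower. How many patients might be affected cannot be estimated from the documents, and no rate is assumed.

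**What to change.** Add to 4.4.1 and 4.6.1, or once in 4.4.2 naming both: *The corticosteroid limits in 4.4.1 and 4.6.1 do not apply to pulmonary events managed under 4.4.2, Table 2 Pneumonitis and Appendix 4, whatever the attribution.*

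The exemption should stop there. The ban on steroid premedication (3.1 and 4.1) and the bar on oral steroids for Grade 1 and 2 rash (5.1.5.2) stay as they are.

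The cost is a minor amendment, which 11.1 requires the coordinating-site IRB to approve before implementation, and a notice to the three sites. It adds no procedures, visits or patients.

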4.4.2. Dose Modifications for Cetuximab-related Non-Immunological Toxicities

If the patient experiences any drug-related event \leq Grade 2, the dose of cetuximab and nivolumab should be continued at the given dose level.

If the patient experiences any drug-related event ≥ Grade 3, the dose of cetuximab and nivolumab should be discontinued until resolution (to baseline) of the toxicities, or until stabilization. Upon resumption, the physician may choose to reduce the dose of Cetuximab per the table below. As an exception, continued treatment in the face of Grade 3 hypomagnesemia and hypophosphatemia will be allowed at the treating physician's discretion. Low magnesium is expected while treating with cetuximab and can be safely replenished as needed throughout treatment according to local guidelines.

If the patient experiences any acute onset or worsening pulmonary symptoms, the doses of cetuximab and nivolumab should be delayed. The management should follow the pulmonary toxicity management as detailed in Section 4.5 Table 2 Pneumonitis and Appendix 4 Pulmonary Adverse Event Management Algorithm because interstitial lung disease from cetuximab and pneumonitis from nivolumab cannot be reliably distinguished.

IND#: Exempt

In the event of Grade ≥ 3 rash, treatment with cetuximab should be paused until recovery to Grade ≤ 2 . Treatment should be resumed at a reduced dose (see Section 4.3). If Grade ≥ 3 rash does not resolve to Grade ≤ 2 within 14 days of stopping cetuximab treatment and despite optimal supportive care, the patient should not receive any further treatment with cetuximab.

In the event of a prolonged (≥7 consecutive days) Grade 2 drug-related toxicities, the investigator may choose to pause cetuximab and nivolumab for up to 4 weeks to allow the patient to recover followed by a dose reduction (the hold and reduction are both at the treating physcian's discretion). Only the cetuximab may be dose reduced, and dose reductions are according to the following table:

	Cetuximab	Nivolumab
	Cycles 1-24 (Q 2 weeks)	Cycles 1-24 (Q 2 weeks)
Dose Level 1	500 mg/m ²	240 mg
Dose Level -1	250 mg/m ²	240 mg
Dose Level -2	125 mg/m ²	240 mg

4.4.3. Infusion Reactions (Cetuximab)

Study Number: MCC 19178

Treatment recommendations are provided below and may be modified based on local institutional standards, package inserts, and guidelines as appropriate.

Monitor subjects for 1 hour following cetuximab infusion on Cycle 1 Day 1 in a setting with resuscitation equipment and other agents necessary to treat anaphylaxis (eg, epinephrine, corticosteroids, intravenous antihistamines, bronchodilators, and oxygen). Monitor longer to confirm resolution of the event in subjects requiring treatment for infusion reactions. Immediately and permanently discontinue cetuximab in subjects with serious infusion reactions. Patients that have tolerated cetuximab infusions well do not require an observation period prior to starting the nivolumab infusion beyond Cycle 1 Day 1.

For Grade 1 symptoms (Mild reaction; infusion interruption not indicated; intervention not indicated):

Remain at bedside and monitor subject until recovery from symptoms. Decrease the cetuximab infusion rate by 50% and monitor closely for any worsening. The total infusion time for cetuximab should not exceed 4 hours.

For Grade 2 symptoms (Moderate reaction requires therapy or infusion interruption but responds promptly to symptomatic treatment [eg, antihistamines, non-steroidal anti-inflammatory drugs, narcotics, corticosteroids, bronchodilators, IV fluids]; prophylactic medications indicated for ≤ 24 hours):

Stop cetuximab infusion, administer bronchodilators, oxygen, etc. as medically indicated, and resume infusion at 50% of previous rate once allergic/hypersensitivity reaction has resolved or decreased to Grade 1 in severity, and monitor closely for any worsening.

For Grade 3 or Grade 4 Symptoms (Severe reaction, Grade 3: prolonged [ie, not rapidly responsive to symptomatic medication and/or brief interruption of infusion]; recurrence of symptoms following initial improvement; hospitalization indicated for other clinical sequelae [eg, renal impairment, pulmonary infiltrates]). Grade 4: (life threatening; presser or ventilator support indicated) Immediately discontinue infusion of cetuximab and disconnect subject from tubing. Begin an IV infusion of normal saline, and treat the subject as follows. Recommend bronchodilators, epinephrine 0.2 to 1 mg of a 1:1,000 solution for subcutaneous administration or 0.1 to 0.25 mg of a 1:10,000 solution and/or diphenhydramine 50 mg IV with methylprednisolone 100 mg IV (or equivalent), as needed. Subjects have to be withdrawn immediately from the treatment and must not receive any further cetuximab treatment. Subject should be monitored until the investigator is comfortable that the symptoms will not recur. Cetuximab will be permanently discontinued.

IND#: Exempt

Investigators should follow their institutional guidelines for the treatment of anaphylaxis. Remain at bedside and monitor subject until recovery from symptoms. In the case of late occurring hypersensitivity symptoms (eg, appearance of a localized or generalized pruritus within 1 week after treatment), symptomatic treatment may be given (eg, oral antihistamine, or corticosteroids).

Once the cetuximab infusion rate has been decreased due to an allergic/hypersensitivity reaction, it will remain decreased for all subsequent infusions. If the subject has a second allergic/hypersensitivity reaction with the slower infusion rate, the infusion should be stopped and cetuximab treatment should be discontinued. If there is any question as to whether an observed reaction is an allergic/hypersensitivity reaction of Grade 1 - 4, the sponsor should be contacted immediately to discuss and grade the reaction.

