Study Design	Each cycle is 4 weeks. Cetuximab is given alone as a lead-in period (Day -14 before Cycle 1 only). Cycle 1 and Day 1 of nivolumab and cetuximab will be given 14 days after the lead-in dose of cetuximab.		
	Pre-medication with steroid before cetuximab and/or nivolumab is not permitted in the trial.		
	Non-steroidal pre-medications are permitted.		
	Phase II Dose level to be determined by the phase I results.		
	Phase I: 3-12 patients Phase II: Cohort A: 45* patients (42 + 3 or 39 + 6)**		
Number of Patients	* 45 evaluable patients will be treated at the MTD. In order to be considered evaluable, patients must complete the lead-in period and receive the C1D1 doses of cetuximab and nivolumab. Non-evaluable subjects will be replaced.		
	** Patients treated at the MTD in the phase I portion of the study will be counted as a part of the phase II patient population.		
	Cohort B: 43 patients		
Description of Cohort A and Cohort B	Cohort A: Patients must have recurrent or metastatic HNSCC that is not amenable to local therapy with curative intent (surgery or radiation therapy with or without chemotherapy). Patients with persistent disease following radiation therapy administered with a chemotherapy sensitizer may also be included. Patients must have progressed on at least one prior line of chemotherapy, targeted therapy, palliative radiation and/or biological therapy regimen for their recurrent and/or metastatic HNSCC. However, if patients are likely to be intolerant to standard first-line systemic chemotherapy, the patients are eligible to		

Study Number: MCC 19178 IND#: Exempt

enroll to this study as the first-line therapy. Additionally, patients with persistent disease or platinum-refractory recurrent disease (recurs within 6 months of last dose of chemotherapy given as a sensitizer to definitive radiation) may enroll in this study as a first-line therapy.

 Prior treatment with a combination of cetuximab and a PD-1/PD-L1 inhibitor is excluded. Prior treatment with cetuximab or a PD-1/PD-L1 inhibitor is allowed as long as not previously given in combination.

Cohort B:

- Patients must have recurrent or metastatic HNSCC that is not amenable to local therapy with curative intent (surgery or radiation therapy with or without chemotherapy).
- Patients with persistent disease following radiation therapy administered with a chemotherapy sensitizer may also be included.

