3.2. DISCUSSION OF STUDY DESIGN

3.2.1. Phase I

This is designed to determine the safety of the cetuximab and nivolumab administration. The purpose of having a lead-in period with cetuximab monotherapy (Day -14 before Cycle 1 only) is to exclude patients with cetuximab-related hypersensitivity reaction before assessing the DLT of the combination regimen.

Eligible patients will begin with a 14-day period with cetuximab alone (Day -14 before Cycle 1 only). This will be followed by subsequent doses of cetuximab and nivolumab starting on Cycle 1 Day 1 IV every 2 weeks in 28-day cycle for 24 cycles or discontinuation per section 3.3.4.

An MRI or CT of neck will be performed approximately every 6 weeks during Cycle 1-3, every 8 weeks during Cycle 5-6 and then every 12 weeks during Cycle 7-24.

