3.2.4. Number of Participants

Phase I: 3-12 patients

Phase II: Cohort A - 45* patients (42 + 3 or 39 + 6)**

* 45 evaluable patients will be treated at the MTD. In order to be considered evaluable, patients must complete the lead-in period and receive the C1D1 doses of cetuximab and nivolumab. Non-evaluable subjects will be replaced.

IND#: Exempt

** Patients treated at the MTD in the phase I portion of the study will be counted as a part of the phase II patient population.

Phase II: Cohort B - 43 patients

* 43 evaluable patients will be treated in Cohort B. In order to be considered evaluable, patients must complete the lead-in period and receive the C1D1 doses of cetuximab and nivolumab. Non-evaluable subjects will be replaced.

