4. TREATMENTS

4.1. CETUXIMAB LEAD-IN PERIOD

Cetuximab will be administered intravenously starting on Day -14 before Cycle 1 only as lead-in period. Starting dose is 500 mg/m² administered with acetaminophen and a histamine H1-receptor antagonist such as cetirizine. Premedication with steroid will not be allowed.

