4.1.1. Definition of Cetuximab Lead-In Toxicity

Study Number: MCC 19178

Patients with grade 3 or 4 infusion reaction must not receive further treatment with cetuximab.

IND#: Exempt

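### Section 4.4.3 gives the one-hour, resuscitation-ready observation after cetuximab for Cycle 1 Day 1 only; the Day -14 lead-in, the first on-study infusion, has no routine observation time

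*Combined protocol and SAP*

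**What the plan says.** The only timed, routine observation after cetuximab is in section 4.4.3: "Monitor subjects for 1 hour following cetuximab infusion on Cycle 1 Day 1 in a setting with resuscitation equipment". It is advice that sites may adapt, because the section opens: "Treatment recommendations are provided below and may be modified based on local institutional standards, package inserts, and guidelines as appropriate". The same paragraph adds that patients who have tolerated cetuximab "do not require an observation period prior to starting the nivolumab infusion beyond Cycle 1 Day 1".

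The synopsis (Study Design) fixes the order of the infusions: "Cycle 1 and Day 1 of nivolumab and cetuximab will be given 14 days after the lead-in dose of cetuximab". Section 4.1 describes the earlier dose: "Cetuximab will be administered intravenously starting on Day -14 before Cycle 1 only as lead-in period". That dose is 500 mg/m², given with acetaminophen and an antihistamine and without steroids. Section 3.2.1 states that the lead-in is there to "exclude patients with cetuximab-related hypersensitivity reaction before assessing the DLT" of the combination. Section 4.1.1 contains one rule: "Patients with grade 3 or 4 infusion reaction must not receive further treatment with cetuximab".

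**The concern.** The lead-in was designed as the dose at which cetuximab hypersensitivity would show itself, so the protocol expects that some patients may react there. Yet the visit with a stated waiting time and stated equipment is the next one, reached by patients who have already come through the lead-in. Followed to the letter, the text lets a patient with no symptoms go home as soon as the first on-study infusion ends, and asks the same patient to stay for an hour after the second.

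What is at stake is patient safety alone: whether a reaction that begins shortly after the first on-study infusion begins where it can be treated. No estimate or test in the statistical section depends on it.

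**Working it through.** No arithmetic applies, and the plan gives no figure to reproduce. The check is to set the sections that govern the two infusions side by side.

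**Step 1: order of the infusions.** The lead-in is on Day -14, and Cycle 1 Day 1 comes 14 days later (synopsis). Cetuximab is given at both, so Day -14 is the first on-study infusion and Cycle 1 Day 1 the second. *First on-study* is not always *first ever*: section 3.3.2 allows prior cetuximab in Cohort A, and in Cohort B when it was given as a radiation sensitizer.

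**Step 2: what each visit is given.**

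| Provision | Day -14 lead-in | Cycle 1 Day 1 |
|---|---|---|
| Routine observation time after cetuximab | none stated | 1 hour (4.4.3) |
| Stated resuscitation-ready setting | none stated | yes (4.4.3) |
| Management once a reaction occurs | yes (4.4.3, no visit named) | yes (4.4.3) |
| Stop cetuximab after a grade 3 or 4 infusion reaction | yes (4.1.1) | yes (3.3.4) |
| Removal for anaphylaxis of any grade | yes (5.1.5.1) | yes (5.1.5.1) |
| Toxicity assessment in the study calendar | yes, no post-infusion time | yes, no post-infusion time |

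**Step 3: what the other safeguards cover.** Section 3.3.3 excludes patients with prior allergic reactions to similar compounds, and section 4.1 requires premedication; both lower the risk. The stopping and removal rules act after a reaction. The grade-specific instructions in 4.4.3 (slow or stop the infusion, give the listed drugs, stay at the bedside, keep monitoring until recovery) begin when symptoms appear. None of them asks a patient without symptoms to wait after the lead-in infusion.

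**Step 4: who is left.** A patient who reacts during the lead-in infusion, or while still on site, is covered by the reaction rules. The patient left uncovered has no symptoms at the end of the infusion, leaves, and reacts afterwards. How often that happens cannot be worked out, because the documents give neither a rate of infusion reactions nor their timing.

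**The case against.** The strongest case on the other side has four parts.

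- **Local practice may already close the gap.** Section 4.4.3 defers to institutional standards, package inserts and guidelines, and any of these may call for observation after a first infusion. This stands as a limit. A reader might infer that patients go unobserved after the lead-in. The documents show only that the protocol is silent there, and the sources it defers to are not part of them.
- **Readiness is implied at every infusion.** A site cannot carry out the 4.4.3 reaction instructions at Day -14 without the drugs and equipment to hand. This stands too, and it reduces the gap to the missing waiting time.
- **Patients with severe lead-in reactions are not the ones left out.** A reader might reason that a grade 3 or 4 reaction at Day -14 ends cetuximab, that evaluable "patients must complete the lead-in period and receive the C1D1 doses of cetuximab and nivolumab" (section 3.2.4), and that those most at risk therefore never reach the visit with the stated hour. That is true as sequence, but the reaction rules apply at any visit and cover these patients once symptoms appear. The argument does not enlarge the gap.
- **The Cycle 1 Day 1 hour may serve as a pause before the first nivolumab dose.** The closing sentence of the paragraph in 4.4.3 supports that in part. It is a reason to keep the hour where it is, and it supplies no instruction for Day -14.

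What survives is that the one routine observation in the protocol names the second infusion and leaves out the screening infusion.

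**Conclusion.** The point holds as a minor omission with a cheap safety remedy. The reading of the text is certain. The practical consequence is not, because it depends on local standards and package inserts that cannot be seen from the documents.

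A reader might also infer that the lead-in fails as a hypersensitivity screen, or that the dose decision is in doubt. Neither follows. Lead-in toxicity is outside the DLT window by design (4.2.3), and the phase II dose was settled in April 2018 on 3 evaluable patients with no DLTs (3.2.2). Better detection is not claimed either: severe reactions are unlikely to go unnoticed, and lead-in adverse events need not be reported (7.2.2, 7.2.5). Power, alpha and the endpoints are untouched.

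No count of reactions averted can be given. The documents do not say how many patients remain to be enrolled, so the number who could benefit may be zero.

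**What to change.** In section 4.4.3, change the visit named in the observation sentence so that it reads 'on the Day -14 lead-in and on Cycle 1 Day 1'. Leave the rest of the paragraph as it stands, including the hour at Cycle 1 Day 1 and the allowance for local standards. A cross-reference from section 4.1 is optional.

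Making the Day -14 hour a fixed minimum in 4.1 is not recommended. It would make the lead-in stricter than Cycle 1 Day 1 and override the protocol's deference to local standards and package inserts, and nothing in the documents shows that deference to be unsafe.

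The change needs approval by the coordinating site IRB (section 11.1) and can travel with the next amendment. Its cost is at most about one hour of chair time, at one visit, for each remaining patient whom the site does not already observe.
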